15.3 Patient Demographics and Other Baseline Characteristics

Summaries of clinical and socio-demographic characteristics will be generated within four groups of patients: (1) All patients who sign informed consent prior to the initiation of standard of care temozolamide and radiation, (2) All patients who start dose intensified TMZ, (3) All patients who receive at least one pp65 DC vaccination, and (4) All patients who receive vaccine 4. Categorical descriptors will be summarized using frequency distributions; whereas, interval variables will be summarized using percentiles, as well as means and standard deviations.

15.4 Treatments

Among patients who initiate dose intensified TMZ, a frequency distribution will be generated for the number of vaccines received by each patient.

15.5 Primary Objective

The primary objective of this study is to determine if Td preconditioning of pp65 loaded DC vaccination with GM-CSF extends survival relative to a historical benchmark.

15.5.1 Variable

Overall Survival (OS) is defined as the time between initiation of dose-intensified TMZ and death, or last follow-up if the patient remains alive at the time of analysis.

15.5.2 Statistical Hypothesis, Model, and Method of Analysis

The Kaplan-Meier estimator will graphically describe OS. Median OS will be estimated, with 95% confidence intervals, as well as 12, 18, 24, 36, and 48-month survival rates. A one-sample logrank test [124, 125] will compare this curve to that reported by Gilbert [126] in which the median OS from the start of adjuvant temozolamide treatment was 14.0 months (95% CI: 12.9 to 14.7 months) for patients with newly diagnosed GBM that are unmethylated. An intent-to-treat approach will be used in analyses.

The statistical hypothesis and power calculations are provided in Section 15.9.

Given the possibility that the characteristics of patients who have enrolled on this protocol differs from that described by Gilbert [127] for RTOG 0825, additional analyses will be conducted using the nomogram published by Gittlemen [128] for RTOG 0525 and 0825. For each patient, the probability of 24-month survival will be estimated from the nomogram based upon the patients' baseline characteristics. From these individualized estimates of 24-month survival, an overall estimate of 24-month survival will be generated with 95% confidence interval. That confidence interval will be compare to the actual 24-month survival confidence interval observed.

15.5.3 Handling of Missing Values, Censoring, and Discontinuation

Patients who withdraw from the study without an allowance for survival follow-up, or are lost to follow-up will have OS censored at the date that the patient was last known alive.

15.6 Secondary Objectives

This study has five secondary objectives. The first 3 secondary objectives examine the impact of functional measures of CMV pp65-loaded DC vaccine efficacy on survival post-vaccine. These measures include migration (Section 15.6.1), fold change in CCL3 (Section 15.6.2), and fold change in pp65 antigen-specific polyfunctionality (Section 15.6.3). Power calculations will be provided for each of the secondary objectives. Power calculations for the three functional predictors of survival post-vaccine 4 will be adjusted to account for multiple comparisons using a Bonferroni correction, and will use a type I error rate of 0.0167.

The other secondary objectives include an assessment of whether the percent of T_{Reg} of CD4+ T cells remains stable or decreases without additional temozolomide after vaccine 1 (Section 15.6.4), and an assessment of the safety of the protocol's treatment regimen (Section 15.6.5).

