8 OBJECTIVES AND ENDPOINTS

Table 1. Objectives and Endpoints

	Objective	Endpoint	Analysis
Primary	Determine if Td preconditioning of pp65 loaded DC vaccination with GM-CSF extends overall survival.	Median survival from initiation of dose intensive adjuvant temozolamide.	See Section 15.5
Secondary	Assess the association between migration of CMV pp65 RNA-pulsed DCs with GM-CSF to site-draining inguinal lymph nodes after Td pre-conditioning and subsequent survival. (PLEASE NOTE: With Protocol v.20220204, this objective has been removed as it was already addressed in a previous study.)	For survival after vaccine 4, the hazard ratio associated with a 1 unit increase in migration, defined as the maximum percentage of ^{111}In -labeled DCs reaching inguinal nodes during the 48 hours after the 4 th vaccination.	See Section 15.6.1
Secondary	Assess the association between CCL3 measured post-Td pre-conditioning and subsequent survival.	For survival after vaccine 4, the hazard ratio associated with a 1-unit increase in CCL3 measured post-Td pre-conditioning at vaccine 4.	See Section 15.6.2
Secondary	Assess the association between fold changes in T cell polyfunctionality and subsequent survival.	Mean fold change from baseline in the frequency of pp65 antigen-specific CD8 ⁺ T cells producing three or more cytokines (IFN γ , CCL3, IL-2, TNF α , CD107a) at leukapheresis 2 $14 \pm (4)$ days after vaccine 3. Mean fold change from baseline in the frequency of pp65 antigen-specific CD8 ⁺ T cells producing three or more cytokines (IFN γ , CCL3, IL-2, TNF α , CD107a) at vaccine 6. For survival after vaccine 4, the hazard ratio associated with a 1-fold increase in the frequency of pp65 antigen-specific CD8 ⁺ T cells producing three or more cytokines (IFN γ , CCL3, IL-2, TNF α , CD107a).	See Section 15.6.3
Secondary	Assess whether T _{Reg} levels remain low without adjuvant temozolamide.	Maximum mean peak increase from vaccine 1 in percent T _{Reg} of CD4 ⁺ T cells.	See Section 15.6.4
Secondary	Assess the safety of DI-TMZ treatment followed by DC vaccination.	Proportion of patients who experience unacceptable toxicity.	See Section 15.6.5
Exploratory	Assess the association CCL3 levels and migration.	Mean fold change in CCL3 between pre- and post-Td pre-conditioning. Correlation between CCL3 change from fold change in CCL3, and migration.	See Section 15.7.1

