15.6.1 Secondary Objective #1: Migration and Survival

PLEASE NOTE: The study originally planned to address secondary objective #1 as described below. However, with the activation of Protocol v.20220204, the plans for examining the relationship between migration and survival have been dropped.

Objective	To assess the association between migration of CMV pp65 RNA-pulsed DCs with GM-CSF to site-draining inguinal lymph nodes after Td pre-conditioning and survival after vaccine # 4.
Analysis Set	All patients who undergo migration studies at vaccine 4. Due to budgetary considerations, only the first 16 patients who reach vaccine 4 will undergo migration studies.
Outcome	Survival from vaccine 4.
Hypothesis	Patients with greater migration will have longer survival.
Analysis Plan	The Cox proportional hazards model will assess the impact of migration on survival after vaccine #4. Migration is defined as the maximum percentage of ¹¹¹ In-labeled DCs reaching inguinal nodes during the 48 hours after the 4 th vaccination. The hazard ratio associated with a 1-unit change in migration will be estimated with 95% confidence intervals.
Power Calculations	Cox proportional hazards model will assess the impact of peak migration at 24 or 48 hours after vaccine 4 on subsequent survival, defined as the time between vaccine 4 and death, or last follow-up if the patient remains alive at the time of analysis. Data from ATTAC [129] show that the standard deviation (SD) for peak migration is 7.86 and that the hazard ratio associated with 1 unit increase in migration is approximately 0.86. Assuming SD=7.86, there would be 80% power to detect a hazard ratio of 0.86 assuming a two-tailed test ($\alpha=0.0167$) within a Cox model after 8 deaths [130, 131]. Assuming the median OS post-vaccine 4 is 24 months, approximately 24 months after the 16 th patient undergoes migration studies will 8 deaths be observed.

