15.6.2 Secondary Objective #2: CCL3 and Survival

Objective	To assess the association between CCL3 measured post-Td administration and survival after vaccine # 4.
Analysis Set	All patients who undergo assessment of CCL3 after Td administration. All patients who reach vaccine 4 when Td is administered will be included in analyses. Forty (40) patients are anticipated.
Outcome	Survival from vaccine 4.
Hypothesis	Greater levels of CCL3 are associated with longer survival.
Analysis Plan	The Cox proportional hazards model will assess the impact of CCL3 on survival post-vaccine 4. The hazard ratio associate with a 1-unit increase in CCL3 will be estimated with 95% confidence intervals.
Power Analyses	Cox proportional hazards model will assess the impact of CCL3 on survival post-vaccine 4. Within ATTAC [129], the standard deviation for CCL3 was 12.9 and the hazard ratio for survival post-vaccine 4 was approximately 0.95 for a 1 unit increase in CCL3. Assuming SD=12.9, there would be 80% power to detect a hazard ratio of 0.95 with a two-tailed test ($\alpha=0.0167$) within a Cox model under these assumptions after 24 deaths [130, 131]. If we assume that the median OS post-vaccine 4 is 24 months, then 24 deaths should be observed approximately 20 months after the 40 th patient receives vaccine 4.

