15.6.3 Secondary Objective #3: Polyfunctionality and Survival

Objective	To assess the association between fold changes in T cell polyfunctionality from baseline to pheresis 2, and survival after vaccine #4.
Analysis Set	All patients who have a baseline (pre vaccine 1) and polyfunctionality assessed at leukapheresis 2 who receive vaccine # 4. Polyfunctionality is assessed at leukapheresis so that results do not reflect the impact of Td-preconditioning post-vaccine 4 assessment of polyfunctionality. Due to budgetary considerations, only the first 24 patients who reach vaccine 4 will be analyzed.
Outcome	Survival from vaccine 4.
Hypothesis	Greater fold changes in polyfunctionality are associated with longer survival.
Analysis Plan	The mean fold change from baseline to leukapheresis 2 will be summarized for the frequency of pp65 antigen-specific CD8 ⁺ T cells producing three or more cytokines (IFN γ , CCL3, IL-2, TNF α , CD107a). Cox proportional hazards model will assess the association between fold change increase between baseline and the leukapheresis 2 in the frequency of pp65 antigen-specific CD8 ⁺ T cells producing three or more cytokines (IFN γ , CCL3, IL-2, TNF α , CD107a), and survival post-vaccine 4. The hazard ratio associate with a 1-unit fold change in polyfunctionality will be estimated with 95% confidence intervals.
Power Analyses	Cox proportional hazards model will assess the impact of fold change of pp65-specific polyfunctional CD8+ T cells between baseline and leukapheresis 2 on survival after vaccine #4. Data from Pro00000580 ERADICATE [132] shows that the SD for fold change in polyfunctionality among vaccinated patients is 1.589, and that the hazard ratio associated with 1 unit increase in fold change is

	approximately 0.609. Assuming SD=1.589, there would be 80% power to detect a hazard ratio of 0.6 assuming a two-tailed test ($\alpha=0.0167$) within a Cox model after 16 deaths [130, 131]. If we assume that the median OS post-vaccine 4 is 24 months, then 16 deaths should be observed approximately 38 months after the 24 th patient receives vaccine 4.

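### Section 15.6 keeps a three-test Bonferroni level, tied only to power, for the two biomarker tests that remain: valid, but it gives up about 4 points of power and leaves the level of the tests themselves unstated

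*Combined protocol and SAP*

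**What the plan says.** The introduction to Section 15.6 counts three functional predictors and attaches the correction to their power calculations, which "will be adjusted to account for multiple comparisons using a Bonferroni correction, and will use a type I error rate of 0.0167". It lists the predictors as follows: "These measures include migration (Section 15.6.1), fold change in CCL3 (Section 15.6.2), and fold change in pp65 antigen-specific polyfunctionality (Section 15.6.3".

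Section 15.6.1 says that with version 20220204 "the plans for examining the relationship between migration and survival have been dropped". Table 1 in Section 8 agrees: "With Protocol v.20220204, this objective has been removed as it was already addressed in a previous study".

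The power rows of Sections 15.6.2 and 15.6.3 still use a two-tailed level of 0.0167, giving 24 deaths for CCL3 and 16 for polyfunctionality. The analysis-plan rows of the same tables give no significance level. For CCL3: "The hazard ratio associate with a 1-unit increase in CCL3 will be estimated with 95% confidence intervals". For polyfunctionality: "The hazard ratio associate with a 1-unit fold change in polyfunctionality will be estimated with 95% confidence intervals".

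**The concern.** Two things do not fit together. First, the divisor of three belongs to a family that the current plan no longer tests. Nothing says that 0.0167 was kept deliberately, and Section 15.2 also still describes migration analyses in the first 16 patients, which suggests an incomplete edit. If so, the two remaining tests are held to a stricter level than a family-wise 0.05 requires.

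Second, the correction is worded as a feature of the power calculations, and the rows that describe the analysis do not carry it over. An analyst could judge a hazard ratio at 0.0167 (the power row), at 0.025 (Bonferroni for the two tests that remain) or at 0.05 (the 95% interval). A p-value between 0.0167 and 0.05 could then be reported either way. This matters because Section 7.2 presents these biomarkers as ones the trial will confirm prospectively, and both sections state directional hypotheses.

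**Working it through.** **Inputs.** CCL3 (15.6.2): SD 12.9, hazard ratio 0.95 per unit, 24 deaths. Polyfunctionality (15.6.3): SD 1.589, hazard ratio 0.6 used for power, pilot hazard ratio 0.609, 16 deaths. Both use 80% power, two-sided.

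**Formulas** (Cox model, continuous covariate):
- Deaths: D = (z(1−α/2) + z(0.80))² / (SD × ln HR)², with z(0.80) = 0.842.
- Power = Φ(√D × SD × |ln HR| − z(1−α/2)).

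**Step 1: reproduce the plan.** 0.05/3 = 0.01667, the stated 0.0167, with z = 2.393.
- CCL3: SD × |ln HR| = 12.9 × 0.0513 = 0.662. D = (2.393 + 0.842)² / 0.662² = 23.9, so 24 deaths, as stated.
- Polyfunctionality at 0.6: 1.589 × 0.511 = 0.812. D = 15.9, so 16 deaths, as stated.

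The plan's counts are therefore correct for 0.0167.

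**Step 2: use the two-test level.** 0.05/2 = 0.025, with z = 2.241.

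| Predictor | Power at 0.0167 | Power at 0.025 | Deaths for 80% at 0.025 |
|---|---|---|---|
| CCL3, HR 0.95, 24 deaths | 80.2% | 84.1% | 21.7, so 22 |
| Polyfunctionality, HR 0.6, 16 deaths | 80.3% | 84.3% | 14.4, so 15 |
| Polyfunctionality, HR 0.609, 16 deaths | 77.6% | 81.9% | 15.3, so 16 |

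The gain is about 4 points of power at the planned deaths. In deaths, it is 2 for CCL3 and 1 for polyfunctionality at 0.6. At the pilot value of 0.609, the requirement at 0.025 is 16, the number the plan already states.

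**Step 3: family-wise error for two tests.**

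| Level per test | Independent tests | Bound under any dependence |
|---|---|---|
| 0.0167 | 1 − 0.9833² = 3.31% | 2 × 0.0167 = 3.34% |
| 0.025 | 1 − 0.975² = 4.94% | 2 × 0.025 = 5% |
| 0.05 (95% interval read as a test) | 1 − 0.95² = 9.75% | 2 × 0.05 = 10% |

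**Step 4: matching intervals.** A two-sided 0.0167 corresponds to a 98.33% interval, 0.025 to 97.5% and 0.05 to 95%. The intervals in the plan therefore match neither the stated level nor the two-test level.

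**The case against.** The case for leaving the text alone has real force.

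- A reader might infer that 0.0167 is now wrong. It is not. It controls family-wise error for two tests with room to spare, and a prespecified level need not be relaxed when one member of the family is dropped. In an open-label, single-arm trial, keeping the stricter level is a defensible caution. This stands.
- The loss is small. Both objectives still meet the plan's 80% target on its own assumptions, and these death counts do not drive the sample size, which Section 15.9 bases on overall survival. This also stands.
- A reader might infer that the plan runs at a 9.75% family-wise error. The documents do not support that. They present the 95% intervals as estimates and nowhere say that excluding 1 declares significance. The figure also assumes independence, whereas the two tests share an outcome and overlapping patients, and Section 15.7.3 expects the markers to be highly correlated. It describes a possible misreading, not the plan.
- A reader might infer that no test level appears anywhere. The power rows do name 0.0167 for the same Cox models. That shows which level the power was computed at. It does not say that the final tests use it, and Section 15.6 limits the correction to power.

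What survives is narrower: an outdated count, an avoidable loss of power, and an analysis level left to inference.

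**Conclusion.** The point holds in a limited form. Section 15.6 applies a three-test correction to a two-test family and does not carry any correction into the analysis plan. Error control is not broken. At 0.0167, family-wise error is at most about 3.3%, and the price is about 4 points of power on each remaining biomarker test. The power figures rest on the plan's pilot SDs and hazard ratios and on its planned deaths. The figure of about 10% is an upper bound that applies only if the 95% intervals are used as tests.

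The level 0.025 is the full-alpha Bonferroni level for two tests, not the only valid one. The primary endpoint, the sample size and the safety rules are unaffected. The change is worth making because it costs almost nothing and removes a choice of threshold that would otherwise be made with the results in view.

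**What to change.** Amend Sections 15.6 to 15.6.3 before any biomarker-survival data are examined. Section 15.8 lets available correlative data inform the interim decision, so the change should precede that look.

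1. In 15.6, replace three functional predictors with two and remove migration from the list.
2. State that the two Cox tests themselves, not only their power calculations, are controlled at a family-wise 0.05, either by Bonferroni at 0.025 two-sided each or by Holm. Holm is at least as powerful as fixed Bonferroni.
3. Restate power at the chosen level. For Bonferroni at 0.025, either keep 24 and 16 deaths and give about 84% power for each (polyfunctionality at hazard ratio 0.6), or give the deaths for 80%: 22 for CCL3, and 15 for polyfunctionality at 0.6 or 16 at 0.609. If the counts change, the months quoted for reaching them need restating too.
4. Label the 95% intervals as unadjusted. Under fixed Bonferroni, 97.5% intervals can be added. They do not match Holm, which can test the second hypothesis at 0.05.
5. Align the CCL3 predictor: the 15.6 introduction calls it a fold change, while 15.6.2 and Table 1 analyse the level measured after Td.

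The cost is SAP wording, with no extra patients, samples or follow-up. If biomarker-survival data have already been examined, loosening the level would look post hoc; keeping 0.0167 with a stated reason, and applying it to the tests, would then be the safer course.

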15.6.1 Secondary Objective #1: Migration and Survival

PLEASE NOTE: The study originally planned to address secondary objective #1 as described below. However, with the activation of Protocol v.20220204, the plans for examining the relationship between migration and survival have been dropped.

Objective	To assess the association between migration of CMV pp65 RNA-pulsed DCs with GM-CSF to site-draining inguinal lymph nodes after Td pre-conditioning and survival after vaccine # 4.
Analysis Set	All patients who undergo migration studies at vaccine 4. Due to budgetary considerations, only the first 16 patients who reach vaccine 4 will undergo migration studies.
Outcome	Survival from vaccine 4.
Hypothesis	Patients with greater migration will have longer survival.
Analysis Plan	The Cox proportional hazards model will assess the impact of migration on survival after vaccine #4. Migration is defined as the maximum percentage of ¹¹¹ In-labeled DCs reaching inguinal nodes during the 48 hours after the 4 th vaccination. The hazard ratio associated with a 1-unit change in migration will be estimated with 95% confidence intervals.
Power Calculations	Cox proportional hazards model will assess the impact of peak migration at 24 or 48 hours after vaccine 4 on subsequent survival, defined as the time between vaccine 4 and death, or last follow-up if the patient remains alive at the time of analysis. Data from ATTAC [129] show that the standard deviation (SD) for peak migration is 7.86 and that the hazard ratio associated with 1 unit increase in migration is approximately 0.86. Assuming SD=7.86, there would be 80% power to detect a hazard ratio of 0.86 assuming a two-tailed test ($\alpha=0.0167$) within a Cox model after 8 deaths [130, 131]. Assuming the median OS post-vaccine 4 is 24 months, approximately 24 months after the 16 th patient undergoes migration studies will 8 deaths be observed.

15.6.2 Secondary Objective #2: CCL3 and Survival

Objective	To assess the association between CCL3 measured post-Td administration and survival after vaccine # 4.
Analysis Set	All patients who undergo assessment of CCL3 after Td administration. All patients who reach vaccine 4 when Td is administered will be included in analyses. Forty (40) patients are anticipated.
Outcome	Survival from vaccine 4.
Hypothesis	Greater levels of CCL3 are associated with longer survival.
Analysis Plan	The Cox proportional hazards model will assess the impact of CCL3 on survival post-vaccine 4. The hazard ratio associate with a 1-unit increase in CCL3 will be estimated with 95% confidence intervals.
Power Analyses	Cox proportional hazards model will assess the impact of CCL3 on survival post-vaccine 4. Within ATTAC [129], the standard deviation for CCL3 was 12.9 and the hazard ratio for survival post-vaccine 4 was approximately 0.95 for a 1 unit increase in CCL3. Assuming SD=12.9, there would be 80% power to detect a hazard ratio of 0.95 with a two-tailed test ($\alpha=0.0167$) within a Cox model under these assumptions after 24 deaths [130, 131]. If we assume that the median OS post-vaccine 4 is 24 months, then 24 deaths should be observed approximately 20 months after the 40 th patient receives vaccine 4.

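### The CCL3 and polyfunctionality Cox models carry no baseline-risk term, so a marker that tracks prognosis can pass as a biomarker; add one prespecified model adjusted for the planned nomogram score

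*Combined protocol and SAP*

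**What the plan says.** Section 15.6.2 states that "The Cox proportional hazards model will assess the impact of CCL3 on survival post-vaccine 4" and asks for one hazard ratio per unit of CCL3 with a 95% confidence interval. Section 15.6.3 follows the same pattern: "Cox proportional hazards model will assess the association between fold change increase between baseline and the leukapheresis 2" is the model, again with one hazard ratio. Neither section names a covariate, a stratification factor or an adjusted sensitivity analysis. The plan does not use the word unadjusted. That reading rests on the absence of any other term and on the event counts, which come out exactly when no other covariate is assumed.

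Section 15.6 sets the level for the three marker objectives: their power calculations "will use a type I error rate of 0.0167".

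Section 15.5.2 plans a baseline risk measure. For each patient, "the probability of 24-month survival will be estimated from the nomogram" from baseline characteristics. Its only stated use is to compare expected with observed 24-month survival.

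On interpretation, Table 1 and the objective rows of Sections 15.6.2 and 15.6.3 speak of association. Section 15.6 goes further and treats the markers as functional readouts of vaccine efficacy with an impact on survival. Section 7.2 wants them confirmed prospectively as predictive biomarkers.

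**The concern.** A patient with a good outlook at baseline may both mount a stronger immune response and live longer. A model containing only the marker then credits the marker with survival that belongs to prognosis. The trial has one arm, so no unvaccinated group would show the same gradient.

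The protocol accepts that immune response can depend on a patient's condition: Section 9.1.3 notes that high-dose steroids impair it. That sicker patients need more steroids is my inference, not a statement in the documents.

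CCL3 is probably the more exposed marker. Section 15.6.2 models its level after Td, although Section 15.6 describes it as a fold change. Polyfunctionality is measured relative to each patient's own value before vaccine 1, which should remove some stable differences between patients.

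At stake is whether a significant hazard ratio is carried into the planning of a later trial as a confirmed biomarker when it only restates baseline risk.

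**Working it through.** **1. The plan's event counts.** Inputs from Section 15.6.2: "the standard deviation for CCL3 was 12.9"; "there would be 80% power to detect a hazard ratio of 0.95 with a two-tailed test"; two-sided alpha 0.0167; "within a Cox model under these assumptions after 24 deaths"; "Forty (40) patients are anticipated". Inputs from Section 15.6.3: SD 1.589, hazard ratio 0.6, same alpha and power, 16 deaths, 24 patients.

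Formula (Hsieh-Lavori): D = (z for alpha/2 + z for power)² / [SD² × ln(HR)² × (1 − R²)], where R² is the share of marker variance explained by other covariates.

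- Numerator: (2.393 + 0.842)² = 10.464.
- CCL3, R² = 0: SD × |ln 0.95| = 12.9 × 0.05129 = 0.6617, squared 0.4378. D = 10.464 / 0.4378 = 23.9, so 24, as stated.
- Polyfunctionality, R² = 0: 1.589 × |ln 0.6| = 1.589 × 0.5108 = 0.8117, squared 0.6589. D = 10.464 / 0.6589 = 15.9, so 16, as stated.

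The counts are right, and they assume no other covariate.

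**2. Size of the confounding.** The documents give neither the prognostic strength of the score nor its correlation with a marker, so both are assumed. I simulated a marker with no effect of its own and a standardised risk score, with survival depending on the score alone. Follow-up stopped at the planned deaths (40 patients and 24 deaths; 24 patients and 16 deaths). Wald tests were two-sided at 0.0167, with 10,000 datasets per setting. Correlation is between marker and good prognosis.

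| Score HR per SD | Correlation | CCL3, marker only | Polyfunctionality, marker only |
|---|---|---|---|
| 1.3 | 0.3 | 2.4% | 2.1% |
| 1.3 | 0.5 | 3.8% | 2.8% |
| 1.5 | 0.3 | 3.3% | 2.7% |
| 1.5 | 0.5 | 6.9% | 4.5% |
| 1.7 | 0.3 | 4.1% | 3.5% |
| 1.7 | 0.5 | 10.8% | 6.7% |
| 2.0 | 0.3 | 5.8% | 4.0% |
| 2.0 | 0.5 | 16.1% | 9.9% |

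With the score in the model, rejection is 1.7% to 2.2% throughout. Separate runs of 2,000 datasets gave 16.7% and 8.5% for the last row.

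In that row the median apparent hazard ratio for a null CCL3 is about 0.73 per SD. Per unit this is exp(ln 0.73 / 12.9) = 0.976, against the planned 0.95. Confounding of this size yields roughly half the planned effect on the log scale (0.0244 / 0.0513 = 0.48).

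**3. Is agreement in sign enough?** A rule that keeps the marker-only test and asks only that the adjusted hazard ratio point the same way removes almost nothing. For CCL3 in the last row, false confirmations fall from about 16% to about 15%. Testing the adjusted coefficient itself at 0.0167 gives about 2%.

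**4. What adjustment does to power.** By the formula, required deaths become D / (1 − R²), and power is Φ(√[deaths × (SD × ln HR)² × (1 − R²)] − 2.393). R² is assumed; a correlation of 0.3 to 0.5 corresponds to 0.09 to 0.25.

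| R² | CCL3 deaths needed | CCL3 power at 24 | Polyfunctionality deaths needed | Polyfunctionality power at 16 |
|---|---|---|---|---|
| 0 | 24 | 80% | 16 | 80% |
| 0.1 | 27 | 75% | 18 | 75% |
| 0.2 | 30 | 69% | 20 | 70% |
| 0.3 | 35 | 63% | 23 | 63% |

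The formula is optimistic at these counts: with a score that predicts nothing, simulated marker-only power is about 71% (CCL3) and 63% (polyfunctionality). In simulation the adjusted CCL3 test has about 54% to 65% power at correlations of 0.5 and 0.3. If marker and score are uncorrelated and the score HR is 2.0, adjustment raises CCL3 power from about 54% to 56% to about 67% to 71%.

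**The case against.** The stated objective for both markers is association. A single-marker Cox model answers that and is the model the event counts were built for. These are secondary objectives with few deaths, and a second coefficient is costliest for polyfunctionality. This stands, and it is why the planned models should remain.

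The bias depends on assumed inputs. Section 11 narrows prognostic spread (unmethylated tumours, KPS of at least 70, residual disease under 1 cm, no multifocal disease), and patients must also reach vaccine 4. At a score hazard ratio of 1.3 the error rate is only about 2% to 4%. This also stands: the problem may be small here.

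A reader might infer that adjustment costs nothing or always gains power. It gains power only when score and marker are uncorrelated and the score is prognostic. In the correlated case, which motivates the point, the adjusted test loses power. Part of the marker-only rejection rate there is bias, but the loss is real.

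A reader might also infer that the score already exists. Section 15.5.2 says it will be estimated, as an additional analysis of the primary endpoint. Since the primary set is everyone who starts dose-intensified TMZ, it should cover those who reach vaccine 4.

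What the objection does not answer is the gap between an unadjusted association and the predictive and efficacy language of Sections 7.2 and 15.6.

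**Conclusion.** The point holds as a weakness in model specification and interpretation; the event counts are correct. Under assumed score hazard ratios of 1.3 to 2.0 per SD and correlations of 0.3 to 0.5, the marker-only test at a nominal 1.67% rejects a null marker in about 2% to 17% of trials for CCL3 and about 2% to 10% for polyfunctionality, against about 2% with the score included. The upper figures need both a strong score and a correlation of 0.5.

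Two stronger readings are not supported. One is that the marker findings will be spurious: the documents contain no estimate of how either marker relates to prognosis. The other is that an adjusted result would establish a predictive or vaccine-specific marker. Adjustment removes only measured baseline prognosis. It does not reach events after baseline, such as later steroid use, and one arm cannot separate a prognostic marker from a marker of vaccine effect.

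**What to change.** - Keep the single-marker models in Sections 15.6.2 and 15.6.3 as the planned tests of association.
- For each marker, prespecify a second Cox model with the marker and the nomogram score as the only added covariate. Enter the score as a named transformation of the predicted 24-month survival probability, such as logit or log(−log). Report both hazard ratios with confidence intervals.
- Describe a marker as associated with survival independently of baseline prognosis only if its adjusted coefficient is significant at 0.0167. Agreement in sign is not enough. Otherwise report an association only.
- Limit the conclusions in Sections 7.2 and 15.6 accordingly: neither model supports a claim of vaccine-specific effect.

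The cost is one extra model per marker from a score the plan already calls for, at 12 deaths per coefficient (24 / 2) for CCL3 and 8 (16 / 2) for polyfunctionality. If marker and score correlate, the adjusted test falls short of 80% power, and the plan should say so. No change in sample size is needed, because the planned tests keep their basis.
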